7.2 Study Schedule

Screening/Baseline Visit (up to 3 months prior to day of surgery)

- Obtain informed consent of potential participant verified by signature on written informed consent for screening form.
- Review medical history to determine eligibility based on inclusion/exclusion criteria.
- Review medications history to determine eligibility based on inclusion/exclusion criteria.
- Perform medical examinations needed to determine eligibility based on inclusion/exclusion criteria.
- Schedule day of surgery where primary intervention will be performed.
- Provide participants with information regarding tranexamic acid, and operative steps for administration of drugs into surgical wound prior to closure.
- Provide participants with log books.
- Randomize patient using sealed envelope method.

Day of Surgery

- Verify patient still meets inclusion/exclusion criteria.
- Administer study treatment
- Patient fills out Day 1 of pain diary

Intermediate Visits

- Participants will be called via phone each day by the study team to ensure they have completed their daily log of numerical pain rating scale and number of pain pills taken.
- They will arrive for an intermediate visit on their first postoperative visit (variable time, between 3-14 days postoperatively). Log books will be collected only after postoperative day 14.

Final Study Visit (up to 6 weeks post surgery)

CONFIDENTIAL

This material is the property of the NYU School of Medicine and Langone Medical Center. Do not disclose or use except as authorized in writing by the study sponsor
Interventional Template Version: 11 January 2019

Pain logs will be collected from participants who have not already returned them to study staff. The participants will be released of their duties to the study once the log books have been returned to the physicians. They will continue their routine follow up per the follow up schedule for each hand surgery procedure. No additional data is collected for study purposes at post-op visits beyond data collected per standard of care.

8 Assessment of Safety

8.1.1 Definition of Adverse Events (AE)

An **adverse event** (AE) is any symptom, sign, illness or experience that develops or worsens in severity during the course of the study. Intercurrent illnesses or injuries should be regarded as adverse events. Abnormal results of diagnostic procedures are considered to be adverse events if the abnormality:

- results in study withdrawal
- is associated with a serious adverse event
- is associated with clinical signs or symptoms
- leads to additional treatment or to further diagnostic tests
- is considered by the investigator to be of clinical significance

8.1.2 Definition of Serious Adverse Events (SAE)

Serious Adverse Event

Adverse events are classified as serious or non-serious. A **serious adverse event** is any AE that is:

- fatal
- life-threatening
- requires or prolongs hospital stay
- results in persistent or significant disability or incapacity
- a congenital anomaly or birth defect
- an important medical event

Important medical events are those that may not be immediately life threatening, but are clearly of major clinical significance. They may jeopardize the subject, and may require intervention to prevent one of the other serious outcomes noted above. For example, drug overdose or abuse, a seizure that did not result in in-patient hospitalization, or intensive treatment of bronchospasm in an emergency department would typically be considered serious.

All adverse events that do not meet any of the criteria for serious should be regarded as **non-serious adverse events**.

8.1.3 Definition of Unanticipated Problems (UP)

Unanticipated Problems Involving Risk to Subjects or Others

Any incident, experience, or outcome that meets all of the following criteria:

- Unexpected in nature, severity, or frequency (i.e. not described in study-related documents such as the IRB-approved protocol or consent form, the investigators brochure, etc)
- Related or possibly related to participation in the research (i.e. possibly related means there is a reasonable possibility that the incident experience, or outcome may have been caused by the procedures involved in the research)

CONFIDENTIAL

This material is the property of the NYU School of Medicine and Langone Medical Center. Do not disclose or use except as authorized in writing by the study sponsor
Interventional Template Version: 11 January 2019

- Suggests that the research places subjects or others at greater risk of harm (including physical, psychological, economic, or social harm).

8.2 Classification of an Adverse Event

8.2.1 Severity of Event

For AEs not included in the protocol defined grading system, the following guidelines will be used to describe severity.

- **Mild** – Events require minimal or no treatment and do not interfere with the participant's daily activities.
- **Moderate** – Events result in a low level of inconvenience or concern with the therapeutic measures. Moderate events may cause some interference with functioning.
- **Severe** – Events interrupt a participant's usual daily activity and may require systemic drug therapy or other treatment. Severe events are usually potentially life-threatening or incapacitating.

8.2.2 Relationship to Study Agent

For all collected AEs, the clinician who examines and evaluates the participant will determine the AE's causality based on temporal relationship and his/her clinical judgment. The degree of certainty about causality will be graded using the categories below.

- **Definitely Related** – There is clear evidence to suggest a causal relationship, and other possible contributing factors can be ruled out. The clinical event, including an abnormal laboratory test result, occurs in a plausible time relationship to drug administration and cannot be explained by concurrent disease or other drugs or chemicals. The response to withdrawal of the drug (dechallenge) should be clinically plausible. The event must be pharmacologically or phenomenologically definitive, with use of a satisfactory rechallenge procedure if necessary.
- **Probably Related** – There is evidence to suggest a causal relationship, and the influence of other factors is unlikely. The clinical event, including an abnormal laboratory test result, occurs within a reasonable time after administration of the drug, is unlikely to be attributed to concurrent disease or other drugs or chemicals, and follows a clinically reasonable response on withdrawal (dechallenge). Rechallenge information is not required to fulfill this definition.
- **Possibly Related** – There is some evidence to suggest a causal relationship (e.g., the event occurred within a reasonable time after administration of the trial medication). However, other factors may have contributed to the event (e.g., the participant's clinical condition, other concomitant events). Although an AE may rate only as "possibly related" soon after discovery, it can be flagged as requiring more information and later be upgraded to "probably related" or "definitely related," as appropriate.
- **Unlikely to be related** – A clinical event, including an abnormal laboratory test result, whose temporal relationship to drug administration makes a causal relationship improbable (e.g., the event did not occur within a reasonable time after administration of the trial medication) and in which other drugs or chemicals or underlying disease provides plausible explanations (e.g., the participant's clinical condition, other concomitant treatments).
- **Not Related** – The AE is completely independent of study drug administration, and/or evidence exists that the event is definitely related to another etiology. There must be an alternative, definitive etiology documented by the clinician.

8.2.3 Expectedness

The Principal Investigator will be responsible for determining whether an AE is expected or unexpected. An AE will be considered unexpected if the nature, severity, or frequency of the event is not consistent with the risk information previously described for the study agent.

CONFIDENTIAL

This material is the property of the NYU School of Medicine and Langone Medical Center. Do not disclose or use except as authorized in writing by the study sponsor
Interventional Template Version: 11 January 2019

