Tranexamic acid: Major risks of tranexamic acid have only been seen in systemic usage. We are using tranexamic acid only topically, in order to minimize side effects that may occur when used systemically. For topical tranexamic acid according to the FDA, the most common adverse reactions are nausea, vomiting, diarrhea, allergic dermatitis, giddiness, hypotension, and thromboembolic events.

Aminocaproic acid: Major risks of aminocaproic acid have only been seen in systemic usage. We are using aminocaproic acid only topically, in order to minimize side effects that may occur when used systemically. For topical aminocaproic acid according to the FDA, it is generally well tolerated. The following adverse experiences have been reported: General: Edema, headache, malaise. Hypersensitivity Reactions: Allergic and anaphylactoid reactions, anaphylaxis. Cardiovascular: Bradycardia, hypotension, peripheral ischemia, thrombosis. Gastrointestinal: Abdominal pain, diarrhea, nausea, vomiting. Hematologic: Agranulocytosis, coagulation disorder, leukopenia, thrombocytopenia. Musculoskeletal: CPK increased, muscle weakness, myalgia, myopathy (see WARNINGS), myositis, rhabdomyolysis. Neurologic: Confusion, convulsions, delirium, dizziness, hallucinations, intracranial hypertension, stroke, syncope. Respiratory: Dyspnea, nasal congestion, pulmonary embolism. Skin: Pruritis, rash. Special Senses: Tinnitus, vision decreased, watery eyes. Urogenital: BUN increased, renal failure. There have been some reports of dry ejaculation during the period of AMICAR treatment. These have been reported to date only in hemophilia patients who received the drug after undergoing dental surgical procedures. However, this symptom resolved in all patients within 24 to 48 hours of completion of therapy.

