8.4.2 Serious Adverse Event Reporting

Unexpected SAEs which are possibly related, probably related, or definitely related will be reported to the IRB using the Reportable New Information (RNI) tool within Research Navigator within 48 hours of study team awareness.

All other SAEs will be documented in the AE/SAE log to be submitted to the IRB at the time of annual continuing review.

CONFIDENTIAL

This material is the property of the NYU School of Medicine and Langone Medical Center. Do not disclose or use except as authorized in writing by the study sponsor
Interventional Template Version: 11 January 2019

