8.5 Study Halting Rules

Administration of study agents will be halted and the study will be discontinued if the PI determines that 3 unexpected and related (possibly related, probably related, or definitely related) AEs have occurred.

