8.6 Safety Oversight

It is the responsibility of the Principal Investigator to oversee the safety of the study. This safety monitoring will include careful assessment and appropriate reporting of adverse events as noted above. Medical monitoring will include a regular assessment of the number and type of serious adverse events.

Data Safety Monitoring

The PI is responsible for conducting systematic and periodic reviews of aggregate data and adverse events in accordance with the data safety monitoring plan. In addition to reviewing AEs, the PI will review assessments of drain site, pain scores, and opioid usage in order to ensure safety of enrolled subjects.

The PI will review all study data and adverse events throughout the study on an annual basis. Administration of study agents will be halted and the study will be discontinued if the PI determines that 3 unexpected and related (possibly related, probably related, or definitely related) AEs have occurred.

A summary of the outcomes of these safety reviews along with accumulated adverse events and deviations will be submitted to the IRB as part of an annual progress report at the time of the Continuing Review submission.

9 Clinical Monitoring

Clinical site monitoring is conducted to ensure that the rights and well-being of human subjects are protected, that the reported trial data are accurate, complete, and verifiable, and that the conduct of the trial is in compliance with the currently approved protocol/amendment(s), with GCP, and with applicable regulatory requirement(s).

CONFIDENTIAL

This material is the property of the NYU School of Medicine and Langone Medical Center. Do not disclose or use except as authorized in writing by the study sponsor
Interventional Template Version: 11 January 2019

Individual subject monitoring for this study will be performed by the PI in an ongoing basis as patients are undergo routine clinical follow-up assessments of their drain sites. We review these clinical assessments and add them to our study data. There are no additional assessments of safety that the patient will need to undergo as part of this study.

10 Statistical Considerations

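### By default, related thromboembolic SAEs in the two antifibrinolytic arms do not count toward the only numeric halting rule and reach the IRB in the annual log

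*Combined protocol and SAP*

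**What the plan says.** Section 8.2.3 leaves expectedness to the PI. An event is unexpected if its nature, severity or frequency "is not consistent with the risk information previously described for the study agent".

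Section 2.4.1 supplies the risk information. On tranexamic acid: "For topical tranexamic acid according to the FDA, the most common adverse reactions are nausea, vomiting, diarrhea, allergic dermatitis, giddiness, hypotension, and thromboembolic events". Its list for topical aminocaproic acid includes thrombosis and peripheral ischemia, stroke, and "Respiratory: Dyspnea, nasal congestion, pulmonary embolism". It names no thromboembolic event for lidocaine, bupivacaine or thrombin.

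Three rules use the definition:

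- Halting (8.5, repeated in 8.6): the study is discontinued "if the PI determines that 3 unexpected and related (possibly related, probably related, or definitely related) AEs have occurred". The rule has no seriousness criterion.
- Prompt reporting (8.4.1, 8.4.2): unexpected events rated at least possibly related go to the IRB within 48 hours. For the rest, 8.4.2 says: "All other SAEs will be documented in the AE/SAE log to be submitted to the IRB at the time of annual continuing review".
- Unanticipated Problems (8.1.3, reported within 24 hours under 8.4.3): the first criterion is "Unexpected in nature, severity, or frequency (i.e. not described in study-related documents such as the IRB-approved protocol or consent form".

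On aggregate review, 8.6 states: "The PI will review all study data and adverse events throughout the study on an annual basis".

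**The concern.** Limiting expedited reports to unexpected events is a defensible convention. Here the same filter also governs the only stopping rule that carries a number. The antifibrinolytics are what arms 3 and 4 add to arm 2, and thromboembolism is a serious harm that the protocol itself lists for them. That harm is left out of the count by default, because it was foreseen. A minor unlisted event counts in full, even in arms 1 and 2, which section 2.2.2 describes as standard of care.

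At stake is how soon anyone outside the study team would learn of a cluster of clots in arms 3 and 4, and whether dosing would pause while it was examined.

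**Working it through.** **Rule trace.** This uses protocol text only and assumes no rate.

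| Events | Listed in 2.4.1? | Halting count (8.5) | 48-hour report | Unanticipated Problem |
|---|---|---|---|---|
| 3 definitely related pulmonary emboli, arm 4 | Yes | 0 by nature | Not by nature | Not by nature |
| 3 related thromboembolic SAEs, arm 3 | Yes, as a class | 0 by nature | Not by nature | Not by nature |
| 3 mild, possibly related, unlisted AEs, any arm | No | 3: study discontinued | Yes | If greater risk is also suggested |

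The wording in 8.2.3 could mean the participant's own regimen or all the agents together. On the first reading the same clot in arm 1 or 2 is unexpected and, if related, counts. On the second it is expected in every arm. The result for arms 3 and 4 is the same on both.

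**Timing.** Recruitment is planned at 2-3 months (5.4), with surgery up to 3 months after the pre-operative visit (5.5).

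- Last surgery: between 2 + 0 = 2 and 3 + 3 = 6 months after first enrolment.
- Assume the annual cycle runs from IRB approval and enrolment starts e months later. The last surgery is then at most e + 6 months after approval, which is no later than month 12 if e is at most 6.
- With e = 0, the review comes 12 − 6 = 6 to 12 − 2 = 10 months after the last dose.

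**Illustrations.** The plan gives no event rate and no operating characteristics for its threshold of 3, so there is no figure to reproduce. All rates below are assumptions. The calculations are exact binomial with one event per patient:

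- P(at least 1) = 1 − (1 − p)^n
- P(at least 2) = 1 − (1 − p)^n − n·p·(1 − p)^(n − 1)
- P(at least 3) subtracts a further [n(n − 1)/2]·p²·(1 − p)^(n − 2)

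*At least one related listed thromboembolic SAE in arms 3 and 4.* Here n = 2 × 10 = 20 as planned; simple randomization (10.1.1) may shift it. The chance is 2.0% at p = 0.1%, 9.5% at 0.5%, 18% at 1%, 33% at 2% and 64% at 5%.

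*Existing rule met by mild, related, unlisted AEs alone.* With n = 40, the chance of at least 3 is 0.7% at a rate of 1%, 4.6% at 2%, 32% at 5% and 78% at 10%.

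*Pause under the proposed rule.* The trigger covers any related SAE in any arm, so n = 40:

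- One event, p = 0.1%: 1 − 0.999^40 = 1 − 0.9608 = 3.9%
- One event, p = 1%: 1 − 0.99^40 = 1 − 0.6690 = 33%
- Two events, p = 0.1%: 1 − 0.96077 − 0.03847 = 0.08%
- Two events, p = 1%: 1 − 0.6690 − 0.2703 = 6.1%

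**The case against.** The strongest reply is that 8.2.3 has three limbs, and a listed event can still be unexpected by severity or frequency. Three pulmonary emboli in arm 4 would be 3 of 10 patients. Section 2.4.1 describes aminocaproic acid as well tolerated in general and attributes its major risks to systemic use, so a PI could reasonably call that frequency inconsistent. For arm 3 only the class of event is listed, which leaves severity open. On tranexamic acid the section also says "Major risks of tranexamic acid have only been seen in systemic usage". This all stands, and it is why the conclusion says by default. Its force is limited: no rate is given, thromboembolic events are placed among the commonest reactions to tranexamic acid, stroke and pulmonary embolism are named outright for aminocaproic acid, and both lists are presented as applying to topical use.

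Second, a reader might infer that every safety safeguard in the protocol depends on unexpectedness. The documents do not support that. Section 5.8 allows suspension for significant or unacceptable risk, with prompt notice to the IRB, and does not confine the decision to the PI. Section 8.6 requires regular assessment of the number and type of SAEs, and section 9 has the PI monitor individual participants on an ongoing basis. None of these sets a threshold, and section 9 frames its monitoring around drain-site follow-up.

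Third, a reader might infer that unseen text cannot matter. It could: a consent form giving a rate for clots would supply a frequency yardstick, and 8.6 refers to a data safety monitoring plan that may be a separate document.

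**Conclusion.** The gap is real as a default. Related thromboembolic SAEs in arms 3 and 4 are expected in nature. Unless the PI decides otherwise on severity or frequency, they add 0 to the halting count, trigger neither the 48-hour nor the 24-hour report, and wait for the annual log. Three mild, possibly related, unlisted events would discontinue the study.

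The stronger statement, that such events can never count or be reported promptly, does not follow. What the plan lacks is a defined trigger for this harm; discretion to act exists.

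The rule trace rests on text alone. The timing result, that all patients may be treated before the first annual review, holds if enrolment starts within about 6 months of IRB approval and runs to schedule. The probabilities rest on assumed rates and show scale only. Such events may well be rare in 20 patients, so this is a cheap improvement to safety oversight and not a flaw that undermines the trial.

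**What to change.** Make two changes:

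- **8.4.2:** report every SAE rated at least possibly related to the IRB within 48 hours, whether or not it is expected.
- **8.5:** keep the 3-event rule and add that enrolment and dosing pause pending IRB review when an SAE rated at least possibly related occurs, whether or not it is expected.

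No new data are needed, since AEs and SAEs are already recorded and graded for severity and relationship (8.2, 8.3). The cost is an occasional pause, at the rates worked out above. If the one-event trigger seems too sensitive, two events lower that cost but let a first related SAE pass without a pause, although it would still be reported within 48 hours. A pause can be lifted once the IRB is satisfied (5.8), whereas the existing rule discontinues the study. Keeping that rule means three mild unlisted events would still end the trial; these changes do not address that side of the imbalance.

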8.3 Time Period and Frequency for Event Assessment and Follow-Up

The occurrence of an AE or SAE may come to the attention of study personnel during study visits and interviews of a study participant presenting for medical care, or upon review by a study monitor. All AEs including local and systemic reactions not meeting the criteria for SAEs will be captured on the appropriate RF. Information to be collected includes event description, time of onset, clinician's assessment of severity, relationship to study product (assessed only by those with the training and authority to make a diagnosis), and time of resolution/stabilization of the event. All AEs occurring while on study must be documented appropriately regardless of relationship. All AEs will be followed to adequate resolution.

Any medical condition that is present at the time that the participant is screened will be considered as baseline and not reported as an AE. However, if the study participant's condition deteriorates at any time during the study, it will be recorded as an AE. UPs will be recorded in the data collection system throughout the study.

Changes in the severity of an AE will be documented to allow an assessment of the duration of the event at each level of severity to be performed. AEs characterized as intermittent require documentation of onset and duration of each episode.

The PI will record all reportable events with start dates occurring any time after informed consent is obtained until 7 (for non-serious AEs) or 30 days (for SAEs) after the last day of study participation. At each study visit, the investigator will inquire about the occurrence of AE/SAEs since the last visit. Events will be followed for outcome information until resolution or stabilization.

All unresolved adverse events should be followed by the investigator until the events are resolved, the subject is lost to follow-up, or the adverse event is otherwise explained. At the last scheduled visit, the investigator should instruct each subject to report any subsequent event(s) that the subject, or the subject's personal physician, believes might reasonably be related to participation in this study. The investigator should notify the study sponsor of any death or adverse event occurring at any time after a subject has discontinued or terminated study participation that may reasonably be related to this study. The sponsor should also be notified if the investigator should become aware of the development of cancer or of a congenital anomaly in a subsequently conceived offspring of a subject that has participated in this study.

